2.1. Primary Objectives

- Test the relationship between ante-mortem flortaucipir F 18 PET imaging and tau neurofibrillary pathology associated with Alzheimer's disease (AD), as measured at autopsy.
- Assess inter-reader reliability.

2.2. Secondary Objectives

- Test the relationship between ante-mortem flortaucipir F 18 PET imaging of an AD pattern with uptake beyond the temporal/occipital regions (i.e., τAD++; see Table 1) and tau neurofibrillary pathology associated with AD, as measured at autopsy.
- Assess inter-reader reliability for scans with an AD pattern that is beyond the temporal/occipital regions (i.e., $\tau AD++$; see Table 1).
- Assess agreement among readers of flortaucipir F 18 PET scans in subjects known to be from the intended population (interpretation of scans from Avid Study ¹⁸F-AV-1451-A05 [A05]).
- Assess intra-reader reliability for scans read twice by each reader.

3. Study Design

All training and reads will be conducted by an imaging contract research organization (CRO) as described in the imaging review charter (IRC). Five readers will be trained in-person on the flortaucipir F 18 PET scan read methodology using the previously developed read method. The training will consist of teaching the readers the steps of interpretation, followed by a practice session using a set of demonstration and practice cases. After the training phase is complete, readers will then independently read 262 scans; 83 from Study ¹⁸F-AV-1451-A16 (A16) and 159 from Study A05.

The study population for Study A16 (¹⁸F-AV-1451-A16: A clinico-pathological study of the correspondence between ¹⁸F-AV-1451 PET imaging and post-mortem assessment of tau pathology) consisted of subjects at the end of life, who were imaged with flortaucipir F 18 and came to autopsy. Subjects were enrolled in the study with the intent of capturing a range of tau neurofibrillary pathology in AD.

The study population for Study A05 confirmatory cohort (¹⁸F-AV-1451-A05: An open label, multicenter study, evaluating the safety and imaging characteristics of ¹⁸F-AV-1451 in cognitively healthy volunteers, subjects with mild cognitive impairment, and subjects with Alzheimer's disease) consisted of subjects with cognitive impairment who had mild cognitive impairment (MCI) or dementia with a suspected neurodegenerative cause, and a Mini Mental State Examination (MMSE) score of 20-27, inclusive. Subjects were imaged with flortaucipir F 18 and followed longitudinally for 18 months to assess the subsequent rate of cognitive decline.

4. Procedures and Methods

4.1. Selection and Number of Investigators (Readers)

Five qualified physicians will perform the blinded reads. Readers will be selected using the following criteria:

- Board Certified in radiology or nuclear medicine
- Experience interpreting PET scans
- Have not received training on the Avid flortaucipir F 18 read methodology

4.2. Selection/Number of Images

Two hundred and forty-two unique scans will be read for this study, comprised of the following:

- All 83 subjects from Study A16 (primary and supplemental) who have a valid scan and autopsy
- All 159 subjects from the Study A05 confirmatory cohort who have a valid scan
- In addition, a sub-set of 20 randomly selected cases will be used for intra-reader reliability purposes for a total of 262 scan reads

4.3. Blinded Read Method

Readers will be blinded to all demographic and clinical data. All readers will be trained inperson on the steps of image interpretation, using a set of demonstration and practice cases, prior to starting their independent reads. A copy of the training materials will be provided to each reader for reference. The read methodology is briefly outlined below.

After scaling images to the cerebellar reference region and selecting an appropriate color scale, regions of the neocortex (the posterolateral temporal [PLT], occipital, parietal, and frontal regions) are evaluated for increased tracer uptake; and scans are interpreted as either not consistent (τ AD-), consistent with an AD pattern (τ AD+), or consistent with an AD pattern and likely to progress (τ AD++) using the criteria shown in Table 1.

Table 1. Clinical Read Method Criteria

Read Outcome		Objective Image Features	
Not consistent with AD pattern (τAD-)		No increased neocortical activity, or increased neocortical activity isolated to the mesial temporal, anterolateral temporal, and/or frontal regions.	
	τAD+	In either hemisphere, increased neocortical activity in the posterolateral temporal (PLT) or occipital region(s).	
AD pattern (τAD)	τAD++	In either hemisphere, increased neocortical activity in the parietal/precuneus region(s), or frontal region(s) with increased uptake in the PLT, parietal, or occipital region(s).	

4.4. Data Collection

Data will be collected using electronic case report forms (eCRFs).

4.5. Good Clinical Practice and Monitoring

All clinical studies performed under the direction of Avid/CRO will be conducted in accordance with applicable regulatory requirements and International Conference on Harmonization, Good Clinical Practice, and Avid/CRO Standard Operating Procedures. Monitoring of study data will be performed by the Imaging CRO and will be performed in accordance with their standard operating procedures.

5. Statistical Methods

5.1. General Statistical Considerations

All statistical analyses will be performed using SAS® version 9.0 or higher. The specific analyses to address the objectives will be described in the Statistical Analysis Plan.

5.2. Population for Analysis

Five readers will independently interpret the flortaucipir F 18 PET scans collected from 2 completed Avid Studies, A16 and A05. No new subjects will be enrolled for purposes of this study. All 83 autopsy scans were collected from Study A16 (67 from main study and 16 from supplementary autopsy cohort (SAC)). All 159 scans from Study A05 confirmatory cohort will be included.

Valid images will be considered unevaluable only if 3 out of 5 independent readers declare the image unevaluable for the same reason. Subjects with invalid or unevaluable PET data will be excluded from analyses. Criteria for declaring an image invalid or not evaluable will be specified in advance in the IRC.

5.2.1. Analysis Population for Scan Accuracy Assessment

Flortaucipir F 18 scan accuracy (sensitivity and specificity) will be assessed using all 83 cases from Study A16 that had an autopsy diagnosis by pathologist panel, including:

- 3 front-runners
- 64 main study autopsy cases
- 16 autopsy cases collected under SAC

5.2.2. Analysis Population for Scan Interpretation Precision Assessment

The precision of flortaucipir F 18 PET scan interpretation will be assessed in 2 ways: interreader (i.e., reader-to-reader) reliability, and intra-reader reliability (i.e., agreement between the repeated reads on same scan from same reader). The inter-reader reliability will be assessed using all 242 scans included for this study (83 Study A16 scans and 159 Study A05 scans). The inter-reader reliability will also be assessed separately on the 159 Study A05 scans (i.e., the targeted population for clinical usage), and on the 83 Study A16 scans. Twenty scans will be randomly selected and will be read twice by the 5 readers in a randomized sequence, along with all the other scans. The repeated reads on these 20 scans will be used to assess the intra-reader reliability.

5.3. Power Analysis

Assuming 80% sensitivity and 80% specificity, 14 TS positive or TS negative cases will be needed to show the lower bounds of 95% confidence interval (CI; 2-sided) greater than 50%, for Page 8 of 15

either sensitivity or specificity, with a Wilson score method to calculate the 95% CI. Out of the 83 Study A16 cases with autopsy results, 47 were neurofibrillary tangle (NFT) stage B3 per pathologist's panel diagnosis (TS positive for primary analysis 1), and 36 were NFT stage B2 or lower (TS negative for primary analysis 1); 41 were high AD neuropathologic change (ADNC) according to panel diagnosis (TS positive for primary analysis 2), and 42 were low to intermediate ADNC (TS negative for primary analysis 2). Therefore, this sample size provides adequate power to assess the accuracy of flortaucipir F 18 PET scan in detecting underlying pathological changes.

Fleiss' Kappa will be used to assess the reader-to-reader consistency in flortaucipir F 18 scan visual interpretation. Five independent qualified physicians will read 242 unique scans (83 autopsy scans from Study A16 and 159 scans from Study A05). Assuming the Fleiss' Kappa is expected to be 0.7, this sample size provides over 90% power in detecting a kappa value greater than 0.6, under a two-sided type I error rate of 0.05.

5.4. Efficacy Analysis.

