5. SAMPLE SIZE JUSTIFICATION

Assuming 80% sensitivity and 80% specificity, 14 truth standard (TS) positive or TS negative cases will be needed to show the lower bounds of 95% confidence interval (CI; 2-sided) greater than 50%, for either sensitivity or specificity, with a Wilson score method to calculate the 95% CI. Out of the 83 A16 cases with autopsy results, 47 were neurofibrillary tangle (NFT) stage B3 per pathologist's panel diagnosis (TS positive for primary objective #1 efficacy analysis #1), and 36 were NFT stage B2 or lower (TS negative for primary objective #1 efficacy analysis #1); 41 were high AD neuropathologic change (ADNC) according to panel diagnosis (TS positive for primary objective #1 efficacy analysis #2), and 42 were low to intermediate ADNC (TS negative for primary objective #1 efficacy analysis #2). Therefore, this sample size provides adequate power to assess the accuracy of flortaucipir F 18 PET scan in detecting underlying pathological changes.

Fleiss' Kappa will be used to assess the inter-reader reliability in flortaucipir F 18 scan visual interpretation. Five independent qualified physicians will read 242 unique scans (83 autopsy scans from study A16 and 159 scans from study A05). Assuming the Fleiss' kappa is expected to be 0.7, this sample size provides over 90% power in detecting a kappa value greater than or equal to 0.60, under a two-sided type I error rate of 0.05.

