10. EFFICACY ANALYSIS

10.1. General Considerations

Categorical variables will be summarized as frequencies and percentages by enrolling diagnostic group (Dementia, MCI, or CN). Continuous variables will be summarized using descriptive statistics (n, mean, median, standard deviation, minimum and maximum) by each diagnostic group.

All inferential statistics will be performed at the 2-sided, 0.05 level of significance.

SAS Version 9.0 or above will be used to perform all analyses.

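### Does the accuracy power statement fail because 14 cases give only 70% power and 80%/80% cannot hold for both truth standards?

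*Protocol*

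**What the plan says.** Protocol 5.3 (Power Analysis) opens with "Assuming 80% sensitivity and 80% specificity, 14 TS positive or TS negative cases will be needed" and gives the purpose as "to show the lower bounds of 95% confidence interval (CI; 2-sided) greater than 50" per cent, "with a Wilson score method to calculate the 95% CI". SAP section 5 says the same: "Assuming 80% sensitivity and 80% specificity, 14 truth standard (TS) positive or TS negative cases will be needed". Neither document attaches a power figure to 14 cases.

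The protocol then lists the autopsy counts. For Primary Analysis 1, "47 were neurofibrillary tangle (NFT) stage B3" and 36 were B2 or lower. For Primary Analysis 2, "41 were high AD neuropathologic change (ADNC) according to panel diagnosis" and 42 were below high. The conclusion follows those counts: "Therefore, this sample size provides adequate power to assess the accuracy of flortaucipir F 18 PET scan". The only numeric power in either section, over 90%, is for Fleiss' kappa.

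Under Protocol 5.4.1.1, both analyses use the same positive call (τAD+ or τAD++) on the same 83 cases. Each is met if the same 3 of 5 readers have both lower bounds at 50% or more. SAP 10.2 requires all three primary analyses to succeed.

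**The concern.** The statement stands under a power heading and leads to a claim of adequate power, so a reader may take 14 as a powered sample size. It is not one.

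The planning rates are also not jointly possible. There are 47 B3 cases but only 41 high-ADNC cases, so at least 47 − 41 = 6 B3 cases count as truth-negative in Analysis 2. A read that detects B3 will tend to call such cases positive, and Analysis 2 scores those calls as false positives. If 80% is too optimistic for Analysis 2 specificity, the weakest of the four accuracy bounds was planned at the wrong rate. Because every primary analysis must succeed, that would lower the chance of overall success without the plan showing it.

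**Working it through.** **Inputs.** From Protocol 5.3: assumed rates 0.80 and 0.80; threshold 50%; Wilson two-sided 95% interval; counts 47/36 (Analysis 1) and 41/42 (Analysis 2). From SAP 10.1: two-sided level 0.05, so z = 1.96.

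**1. The figure of 14.** With x correct out of n and p = x/n, the Wilson lower bound is

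[2np + z² − z√(z² + 4np(1−p))] / [2(n + z²)].

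Take the whole number of correct reads at or just below 80%:

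- n = 13: 10/13 gives 49.7%, which fails.
- n = 14: 11/14 gives 52.4%, which passes. Every n from 14 to 21, the range checked, also passes.

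So 14 reproduces as the size at which an observed rate near 80% clears 50%.

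**2. Power at 14.** The rule needs 11 of 14, since 10/14 gives 45.4%. P(X ≥ 11 | n = 14, p = 0.80) = 69.8%. For two independent bounds it is 0.698² = 48.7%. The smallest n with 80% exact power for one bound is 19.

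**3. Power at the actual counts, true rate 80%, one reader.**

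| Bound | n | Correct needed | Power |
|---|---|---|---|
| Analysis 1 sensitivity | 47 | 31 | 99.3% |
| Analysis 1 specificity | 36 | 24 | 98.2% |
| Analysis 2 sensitivity | 41 | 27 | 99.0% |
| Analysis 2 specificity | 42 | 28 | 98.7% |

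**4. Consistency of the rates.** Expected positive reads among the 83 cases:

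- Analysis 1 at 80/80: 0.8×47 + 0.2×36 = 37.6 + 7.2 = 44.8.
- Analysis 2 at 80/80: 0.8×41 + 0.2×42 = 32.8 + 8.4 = 41.2.

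The reads are the same, so both totals cannot hold. With Analysis 1 fixed at 80/80, the counts impose one equation on Analysis 2: 41×sens₂ + 42×(1 − spec₂) = 44.8. Solutions include:

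- sens₂ = 80%: spec₂ = 1 − (44.8 − 32.8)/42 = 71.4%.
- sens₂ = 85%: spec₂ = 76.3%.
- sens₂ = 88.8%: spec₂ = 80%.

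Starting instead from 80/80 in Analysis 2, with Analysis 1 sensitivity at 80%, Analysis 1 specificity is 1 − (41.2 − 37.6)/36 = 90%.

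**5. Effect of 71.4%.** Assume that every high-ADNC case is B3, which the documents do not state. The 42 Analysis 2 negatives are then 36 non-B3 cases and 6 B3 cases. With 80% of the six read positive, specificity is (36×0.8 + 6×0.2)/42 = 30/42 = 71.4%, and P(at least 28 of 42 correct) for one reader is 83.4%. Treating all 42 as alike gives 80.5%. Other positive rates among the six give:

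| Positive among the six | Specificity | Power, one reader |
|---|---|---|
| 20% | 80.0% | 98.7% |
| 50% | 75.7% | 94.1% |
| 80% | 71.4% | 83.4% |
| 95% | 69.3% | 74.9% |

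**6. The decision rule itself.** Five readers were simulated with beta-binomial reads within the 41/6/36 strata, requiring both bounds in at least 3 readers. A within-stratum correlation of 0.53 corresponds to the plan's kappa, since (0.09 + 0.53×0.16)/0.25 = 0.70. At 71.4% specificity, Analysis 2 then succeeds with about 87% probability, against about 99% for Analysis 1. Over correlations from 0.8 to 0, Analysis 2 runs from about 84% to 96%. Letting specificity range from about 70% to 80% as well widens this to about 79% to nearly 100%.

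**The case for a change.** The strongest case for a change is that 71.4% is not arbitrary. It follows from keeping three of the plan's four rates at 80%. The route that restores 80% specificity needs sens₂ = 88.8%. If high-ADNC cases are all B3, that leaves only 37.6 − 36.4 = 1.2 of the six B3-but-not-high cases read positive, or 20%. This is the false-positive rate assumed for B0–B2 scans, whereas Analysis 1 assumes B3 scans are called positive 80% of the time. On that view the plan understates the chance of missing Analysis 2: about 13% rather than about 1%. Stating power for the real rule, and listing B3-but-not-high false positives separately, would cost little.

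Some of this stands. Analysis 2 specificity is the bound most likely to fall short, the shared 80/80 assumption is loose, and the text would be clearer if 14 were labelled a precision threshold. But the counts alone do not give 71%. They fix one equation in two unknowns, and all four rates can be 80% or more together. The plan also sets no numeric power target for accuracy, so even the unfavourable scenario contradicts nothing it states. The separate line of false positives is a reporting preference and corrects no error.

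**Conclusion.** No change follows. The figure of 14 is correct as a Wilson precision threshold, and the design does not rest on it: the smallest class has 36 cases, and power per bound at a true 80% is at least 98.2%. The 80/80 assumption applied to both standards is a simplification that cannot hold exactly, by 44.8 − 41.2 = 3.6 expected positive reads out of 83. Placing all of that on Analysis 2 specificity weakens the claim of adequate power but does not overturn it: 83.4% for one reader on that bound, and about 84% to 96% for the three-of-five rule. Those last figures assume that high-ADNC cases are nested within B3 and that within-stratum reader correlation lies between 0.8 and 0.

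No design choice depends on the answer. Protocol 4.2 and 5.2 take every Study A16 autopsy case with a valid scan and enrol no one new, so the sample cannot be enlarged within this plan. The endpoints, intervals, success rule and interpretation would be the same under any rewording. This is a loosely worded justification for a fixed sample.

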5.4.1. Primary Analyses

The primary objectives for this study are to assess both the accuracy and precision of flortaucipir F 18 PET imaging to detect tau neurofibrillary pathology associated with (AD).

5.4.1.1. Assessing the Accuracy of Flortaucipir F 18 PET Scan

Analyses for Primary Objective 1:

For the first primary objective, 2 analyses will be planned to assess the accuracy of flortaucipir F 18 PET imaging in detecting tau pathology, as measured at autopsy.

Primary Analysis 1

The diagnostic performance (sensitivity/specificity) of 5 independent readers' interpretations of ante-mortem flortaucipir F 18 PET imaging for detection of a pattern of flortaucipir F 18 neocortical uptake that corresponds to NFT Score of B3 (Hyman et al. 2012; Montine et al. 2012) at autopsy will be evaluated; and

Primary Analysis 2

The diagnostic performance (sensitivity/specificity) of 5 independent readers' interpretations of ante-mortem flortaucipir F 18 PET imaging for detection of a pattern of flortaucipir F 18 neocortical uptake that corresponds to high levels of AD neuropathologic change as defined by National Institute on Aging-Alzheimer's Association (NIA-AA) criteria (Hyman et al. 2012) will be evaluated. For individuals with cognitive impairment, high levels of AD neuropathologic change are considered adequate to explain cognitive impairment or dementia symptoms.

For Primary Analysis 1, the hypothesis to be tested is that for the same 3 out of 5 independent readers; the lower bound of the two-sided 95% CI for both sensitivity and the specificity of flortaucipir F 18 PET reading results will be ≥50%. As detailed in Section 5.4.1, Table 2, NFT scores for autopsy cases will be categorized as either B0/B1/B2 or B3 level; and will serve as the NFT Score TS for this analysis. Flortaucipir F 18 PET imaging will be classified by each reader

as either neocortical uptake not consistent with AD (τ AD-), or neocortical uptake consistent with AD (τ AD+) or neocortical uptake consistent with AD and likely to progress (τ AD++). Sensitivity and specificity will be calculated for each reader as the proportions of true positive (TP) and true negative (TN) cases correctly identified as such, according to Table 2 below:

Table 2. Primary Objective 1 Analysis 1: Diagnostic Performance
Calculations for flortaucipir F 18 PET Scan Reader Interpretation
vs. Autopsy NFT Score Truth Standard

	Autopsy NFT Score TS	
Physician Reader Interpretation	NFT Score B3 [Truth Positive]	NFT Score B0–B2 [Truth Negative]
Flortaucipir F 18 neocortical uptake; AD pattern (τAD+/τAD++)	True Positive (TP)	False Positive (FP)
Flortaucipir F 18 neocortical uptake not consistent with AD (τAD-)	False Negative (FN)	True Negative (TN)

Two-sided 95% CIs for sensitivity and specificity will be calculated using the Wilson score method. The first primary endpoint is considered to be met if for the same 3 out of 5 readers, the lower bound of the 95% CIs for both sensitivity and specificity are \geq 50% (i.e., statistically significant at two-sided significance level of 0.05).

Like Primary Analysis 1, the hypothesis to be tested for Primary Analysis 2 is that for the same 3 out of 5 readers, the lower bound of the 95% CIs for both sensitivity and the specificity will be ≥50%. For Primary Analysis 2, autopsy cases will be categorized as either not, low, or intermediate versus high level of AD neuropathologic change according to NIA-AA criteria, considering Braak stage, Thal plaque score, and Consortium to Establish a Registry for Alzheimer's Disease (CERAD) amyloid neuritic plaque score, and this level of AD neuropathologic change will be used as the NIA-AA autopsy diagnosis TS as detailed in Section 5.4.1 Table 3. Flortaucipir F 18 PET images will be interpreted by visual examination as either τAD- or τAD+/τAD++ as for Primary Analysis 1. Sensitivity and specificity will then be calculated for each reader as the proportions of TP and TN cases correctly identified as such, according to Table 3 below:

Table 3. Primary Objective 1 Analysis 2: Diagnostic Performance
Calculations for Flortaucipir F 18 PET Scan Reader Interpretation
vs. NIA-AA Autopsy Diagnosis Truth Standard

	NIA-AA Autopsy Diagnosis TS		
Physician Reader Interpretation	High AD Neuropathologic Change [Truth Positive]	Not, Low, or Intermediate AD Neuropathologic Change [Truth Negative]	
Flortaucipir F 18 neocortical uptake; AD pattern (τAD+, τAD++)	True Positive (TP)	False Positive (FP)	
Flortaucipir F 18 neocortical uptake; not consistent with AD pattern (τAD-)	False Negative (FN)	True Negative (TN)	

Two-sided 95% CIs will be calculated using the Wilson score method. The second primary endpoint is met if for the same 3 out of 5 readers, the lower bounds of the 95% CIs for both sensitivity and specificity are \geq 50%.

The pathological diagnosis (for both NFT score TS and NIA-AA autopsy diagnosis TS) for Study A16 SAC cases were based on tissue samplings from 1 side of brain. Therefore, the reads from the corresponding hemisphere upon which the pathological diagnosis was based on will be used for primary analyses 1 and 2.

5.4.1.2. Assessing the Precision of Flortaucipir F 18 PET Scan Reads

The second primary objective will assess inter-reader reliability.

Primary Objective Analysis 2

The inter-reader reliability of flortaucipir F 18 PET scan visual interpretation will be assessed using kappa statistics. Fleiss' Kappa and the associated 95% CI will be calculated based on 5 readers' visual interpretations on the 242 scans (comprised of 83 scans from Study A16 autopsy cases, and 159 cases from Study A05). The p-value will be calculated using normal approximation method. The lower bound of the 95% CI for Fleiss' Kappa must be greater than or equal to 0.6 to meet the inter-reader reliability criterion. If the scan is selected (by random) to be read twice for the intra-reader reliability assessment, the first read will be used for the second primary objective analysis; for Study A16 SAC cases; the overall reads (using both hemispheres) from each reader will be used for the second primary objective analysis.

